4.3. Safety Endpoint

Incidence of heart graft-related Serious Adverse Events (SAEs) in the first 30 days post heart transplantation, defined as:

 Moderate or Severe Primary heart graft dysfunction (PGD) (left or right ventricles) (not including rejection or cardiac tamponade). Please see Appendix 2 for detailed definition of LV and RV PGD according to ISHLT consensus manuscript. Primary graft failure requiring re-transplantation

5. TRIAL POPULATION

The trial will include 55 heart transplant recipients, at up to 20 investigational sites in the U.S. and world-wide (Europe, Australia, and Canada).

5.1. Donor Eligibility Criteria

5.1.1. Donor Inclusion Criteria

Donor hearts are required to meet at least one of the following inclusion criteria:

- Expected total cross-clamp time of ≥ 4 hours
- Expected total cross-clamp time of ≥ 2 hours PLUS one of the following risk factors:
 - Donor age 45-55 years old with no coronary catheterization data; or
 - Donor age \ge 55 years old; or
 - Left ventricular septal or posterior wall thickness of $>12 \le 16$ mm; or
 - Reported down time of ≥ 20 min, with stable hemodynamics at time of final assessment; or
 - Left heart ejection fraction (EF) $\geq 40 \leq 50\%$; or
 - Donor angiogram with luminal irregularities with no significant CAD
 - Death caused by carbon monoxide poisoning with good cardiac function at time of donor assessment
 - Social history of alcoholism with good cardiac function at time of donor assessment; or
 - History of diabetes combined with negative coronary angiogram for coronary artery disease (CAD).

5.1.2. Donor Exclusion Criteria

Donor hearts will be excluded if they meet any of the following criteria:

- Angiogram proven CAD with > 50% stenosis; or
- Cardiogenic shock or myocardial infarction; or
- Sustained terminal EF of < 40%; or
- Significant valve disease except for competent bicuspid aortic valve.

5.2. Recipient Eligibility Criteria

5.2.1. Recipient Inclusion Criteria

Recipients are required to meet all the following criteria on the day of transplant:

- Registered primary heart transplant candidate
- Age ≥ 18
- Signed: 1) written informed consent document and 2) authorization to use and disclose protected health information.

5.2.2. Recipient Exclusion Criteria

Recipients will be excluded if they meet any of the following criteria on the day of transplant:

- Prior solid organ or bone marrow transplant
- Chronic use of hemodialysis or diagnosis of chronic renal insufficiency
- Multi-organ transplant.

6. PRE-OPERATIVE TRIAL PROCEDURES

6.1. Subject Identification

All patients on the transplant waiting list who are being treated by trial investigators will be identified. Those patients who initially appear eligible for the trial will have the trial thoroughly explained to them, be invited to participate, and will be asked to sign an informed consent for participation in the trial prior to treatment. When a matching donor heart becomes available, the inclusion and exclusion criteria will be re-verified. When a final decision is made at the recipient site to transplant the heart, the recipient will be assigned a subject identification number.

6.2. Recipient Day of Transplant Assessment

The purpose is to conduct a final assessment of whether the potential consented recipient still meets the eligibility criteria. The following information will be verified and recorded on the day of transplant:

• **Eligibility:** Investigator will review and confirm that the potential consented recipient continues to meet all inclusion criteria and no exclusion criteria.

• Demographics/Characteristics:

- Date of birth or Age
- Gender, body mass index
- Race and Ethnicity
- Blood type and RH factor
- Date of listing on the national heart transplant waiting list

- Date of consent to the EXPAND Trial
- Recipient ID
- Recipient allocation urgency status

• Recipient Risk Factors & Medical History:

- Indication for transplantation: The primary etiology of heart failure will be recorded
- Presence of Circulatory Mechanical Support (LVAD, RVAD or total artificial heart) will be recorded. Type, brand, and date of insertion will be recorded
- Panel reactive antibody %
- Use of mechanical ventilation prior to transplantation
- History of diabetes and type of treatment (insulin vs. oral hypoglycemic agents)

6.3. Donor Screening and Acceptance

Using the inclusion and exclusion criteria, the investigator or a member of her/his transplant team will evaluate the donor and the quality and suitability of the hearts for the trial. The following evaluations will be conducted and recorded:

- Organ Donor Identification Number and Type of Registry (e.g., UNOS ID, Eurotransplant ID)
- **Demographics:** Age, Date of birth (if available), gender, race, and ethnicity
- **Donor Characteristics:** Blood type & RH factor, body mass index
- Donor's Cause of Death:
 - Cause of death and date and time of pronouncement of brain death
 - Documented cardiac arrest witnessed or not and estimated down time
 - History of chest trauma and any evidence of sternum or rib fractures

• Medical History:

- Active infection, positive serology for CMV, HIV, Hepatitis B or C, malignant tumors, and heart disease
- History of diabetes

• Social History:

- History of drug abuse or cocaine
- Smoking
- **Donor Heart assessment:** The donor heart will be assessed prior to procurement and acceptance using the following methods:
 - Angiogram findings (if available): Evaluated for any potential pathology (e.g., coronary artery disease).

- ECHO findings (if available): EF, wall motion, LV septum and wall thickness, and any valvular abnormalities.
- Final inspection and palpation prior to acceptance in the chest: The donor heart will be evaluated for any contusions or any gross abnormalities.
- Eligibility: The donor will be evaluated to document whether the eligibility criteria
 are met. All eligibility criteria or clinical reasons for not accepting a donor heart at
 final assessment before retrieval will be recorded.

6.4. Donor Heart Retrieval and OCSTM Preservation and Assessment

After final evaluation of the donor heart in donor's chest and upon acceptance into the trial, the investigators will retrieve and preserve the donor heart according to the following protocol:

• Initial Heart Flush in Donor Body: all donor hearts will be arrested using 750-1000 ml of cold Del Nido heart arrest and flush solution OR identical chemical formulation (see below) flush via the aortic root according to standard retrieval procedure.

Del Nido Solution Formulation	Concentration
Base Solution 1 Liter	Components (mmol/L)
Na	140
Cl	98
K	5
Mg	3
Acetate	27
Gluconate	23
рН	7.4 (6.5-8)
Additives	(ml/L base solution)
KCL 2mEq/L	13
NaHCO3 1mEq/ml	13
MgSO4 50% - 0.5 g/ml	4
Lidocaine 1%	13
Mannitol 20%	16

- OCSTM Heart Perfusion: The OCSTM Heart system will be primed using:
 - 1.2-1.5 L of donor blood
 - 100-300 ml of 25% albumin solution
 - 300-500 ml of OCS™ Heart priming solution
 - Hearts preserved on the OCSTM Heart should be maintained according to the OCSTM Heart Instructions for use (IFU).

- Lactate Level and other chemistries sampling scheme: The organ retrieval team will collect samples from the donor and from the arterial and venous ports of the device and measure lactate levels using a standard blood gas analyzer according to the following protocol:
 - One blood sample will be collected from the donor prior to cross clamp (Donor Baseline Sample)
 - One blood sample will be collected after the donor's blood is added to the OCS™ circuit and prior to instrumentation of the donor's heart (Pre-instrumentation Sample).
 - One arterial and one venous sample will be collected within 10-20 minutes of perfusing the heart on the OCSTM Heart device.
 - At least, one additional arterial and venous sample will be collected before leaving the donor site.
 - Samples will continue to be collected from the device at approximately hourly intervals and after any active CF adjustment or any other adjustments.
- The OCSTM Heart Preservation Parameters: The OCSTM device parameters should be maintained within the following ranges after stabilization of the organ
 - Aortic Pressure (mean AOP): 40-100 mmHg
 - Coronary Flow (CF): 400-900 ml/min
 - Perfusate Temperature (Temp): 34°C
 - Circulating total Lactate (Lact): < 5 mmol/L

The ranges above represent the optimum perfusion values for the majority of the organs previous maintained on the OCSTM Heart System. However, the user may modify these parameters to achieve adequate preservation conditions for an individual organ.

- OCSTM Device Malfunction(s): will be recorded.
- **Final Heart Cooling and Flush Arrest on OCS**TM: All donor hearts on OCSTM will be cooled down gradually to perfusate Temp. of 10-14°C using standard water cooler, followed by cold flush using 1 L of cold Del Nido arrest and flush solution OR identical chemical formulation (see above) flush according to the following protocol:
 - Use standard clinical cardiopulmonary bypass water heater-cooler device (for example Stöckert Heater-Cooler System 3T, Maquet HCU 30, or equivalent device) to perform the cool down protocol.
 - Set the water temperature of the water Heater-Cooler device to 34°C (similar to OCSTM Heart temperature).
 - Once at 34°C, connect the water Heater-Cooler water lines to the OCS™ Heart oxygenator water lines and start circulation.
 - Set the OCSTM heater temperature to Off.

- Immediately lower the water Heater-Cooler device temperature by up-to 10°C lower than OCSTM temperature (for example, if OCSTM temp is 34, the water Heater-Cooler should be at 24°C) and reduce OCSTM pump flow by 100 mL/minute.
- As the temperature displayed on the OCS[™] Monitor approaches the Heater-Cooler water temperature set point (within 1-2°C), lower the Heater-Cooler water temperature by up to 10°C and reduce OCS[™] pump flow by 100 mL/minute to allow the perfusate & organ to continue cooling.
- Repeat this process until the desired target perfusate temperature (10-14°C is achieved, as displayed on the OCS™ Monitor.
- Connect the cold cardioplegia bag to the aortic root port as per the OCS™ IFU.
- Start administering the cold arrest & flush solution to the aortic root.
- Turn off the OCSTM pump as per the OCSTM IFU.
- **Myocardial Protection of Donor Heart During Re-implantation:** Adequate myocardial protection:
 - Intermittent doses of antegrade (Aortic root) blood based cardioplegia every 20-30 minutes. Venting of the LA to avoid heart rewarming.
 - Reperfusion for at least 30 minutes prior to weaning from cardiopulmonary bypass.
- **Donor Retrieval Details:** The following information will be collected at time of heart retrieval
 - Date and time of cross clamp of donor aorta.
 - Need for external pacing will be recorded.
- OCSTM Parameters and Enabled Measurements: The following OCSTM Heart perfusion parameters and heart metabolic conditions will be recorded:
 - AOP
 - CF

(AOP and CF are system data collected by the device during the preservation run and uploaded directly into the database)

Lactate level

6.5. Donor Heart Acceptance for Transplantation

- To maximize safety to potential recipients, the surgical procedure should not be initiated on the recipient until the donor heart has been clinically accepted by the transplanting surgeon/physician based on the below acceptance criteria.
- All donor hearts preserved on OCSTM Heart must meet the following clinical criteria for transplantation at final assessment on OCSTM Heart (Final Sample):

- Final total arterial circulating OCSTM Heart perfusate Lact. Level < 5 mmol/L with stable lactate trend.
- Stable CF, AOP trends within above ranges (certain expanded criteria organs, i.e., LVH hearts, may require higher CF and/or AOP to achieve adequate perfusion).
- Any decision to turn down hearts after the hearts have been retrieved, preserved and assessed on OCSTM Heart should be done with notification to the Site PI and the donor heart must be examined by the transplant center's qualified cardiac transplant pathologist and a central core lab for further assessment to evaluate any inherent cardiac pathology that was not diagnosed at retrieval of the donor heart.

7. TRANSPLANT, IMMEDIATE POST-OPERATIVE AND LONG-TERM FOLLOW-UP

7.1. Transplant Details

The following information concerning the transplant procedure will be collected:

- The organ recipient unique post-transplant patient identifier
- Total cross clamp duration in minutes (from donor cross-clamp application to removal of cross-clamp in the recipient)
- Post-OCSTM cold ischemia time (time from heart flush on OCSTM until aortic cross-clamp removal in the recipient)
- Any surgical complications encountered during surgery

7.2. Post-Transplant Functional Assessments Day 0 – Day 30

- Heart Primary Graft Dysfunction (PGD) Surveillance in the first 24 hours (see Appendix 1):
 - Initial use of Mechanical Circulatory Support: The use of ECMO, intra-aortic balloon, LVAD, RVAD, or bi-VAD will be recorded
 - Inotropic Support for first 72 hours: The following inotropic medication doses will be collected at ICU admission T0, T12, T24, T48, and T72 hours after ICU admission post-heart transplantation:
 - *Dopamine mcg/kg/min*
 - *Dobutamine mcg/kg/min*
 - *Amrinone mcg/kg/min*
 - Milrinone mcg/kg/min
 - Epinephrine *mcg/kg/min*
 - Norepinephrine *mcg/kg/min*
 - Right Heart Catheter Data between at ICU admission T0, T12, T24, T48 and T72 hours after ICU admission post-heart transplantation (if applicable):
 - Pulmonary Artery Pressures (PAP)
 - Pulmonary Capillary Wedge Pressure (PCWP)

- Cardiac index (CI)
- Right Atrial Pressure (RAP)
- **Initial use of Mechanical Respiratory Support:** Duration of initial post-transplant invasive ventilator support will be recorded from the time of initial admission to ICU post-heart transplant until extubation.
- Initial Post-Transplant ICU Stay: Intensive care unit (ICU) admission time, and date and time when clinical order for ICU discharge is written.
- **Immunosuppression Medications:** The type of immunosuppression medication and dose will be recorded at day 7 and at time of discharge from the hospital. Immunosuppression induction will be recorded if applicable.
- Trans-thoracic echocardiogram results prior to Discharge will be recorded:
 - Ejection Fraction (EF%)
 - Wall motion assessment
 - LV Septal and posterior wall thickness
 - Any valve abnormalities
- Patient and Graft Survival at Day 30: Patient and graft survival will be assessed on day 30 post-transplant.
- Adverse Events: All heart graft-related serious adverse events and any heart graft-related adverse events will be followed and documented until the investigator designates the event to be either resolved or its effect on the patient's condition stabilized.
- **Medications:** Medications used to treat all serious heart graft-related adverse event (SAE)-related will be recorded in the trial electronic database until the SAE is resolved

These follow-ups will be attempted within \pm 3 days of the designated periods expect for the PGD Surveillance in the first 24 hours which must be collected at the designated times. The evaluations may be conducted over several days.

7.3. Long-Term Follow-up: 6 and 12 months

Follow-up data collection will be conducted at approximately 6 and 12 months post-transplant.

- **6-month Follow-Up:** At approximately 6 months post-transplant, the patient will be evaluated at an office visit if this is the institution's standard of care, and, if not, by phone contact by the site. The patient's medical record may be reviewed to confirm patient's answers. This follow-up will collect information on:
 - Patient and graft survival;
 - Whether the patient was re-hospitalized after initial discharge, and, if so, the primary reason for the hospitalization and the length of stay;
 - Information will also be collected on any diagnosis of cardiac dysfunction and, if so, the method of diagnosis and treatment.

The 6-month follow-up will be collected within ± 1 month of the designated period and will be recorded on the 6-month follow-up electronic form.

- 12-month Follow-Up: At approximately 12 months post-transplant, the patient will be evaluated at an office visit if this is the institution's standard of care, and, if not, by phone contact by the site. The patient's medical record may be reviewed to confirm patient's answers. This follow-up will collect information on:
 - Patient and graft survival
 - Results of standard of care coronary angiogram and right heart catheterization will be collected
 - Any diagnosis of cardiac allograft vasculopathy and, if so, the method of diagnosis (e.g., IVUS, coronary angio).

The 12-month follow-up will be collected within \pm 1 month of the designated period and will be recorded on the 12-month follow-up electronic form.

8. EVALUATION OF ADVERSE EVENTS

8.1. Evaluation of Heart Graft-Related Adverse Events

Heart Graft-Related Adverse Events are those which have any untoward effect on the health or safety of the patient and that are related to the transplanted heart function (except for acute rejection or myocardial tamponade). Heart graft-related adverse events will be collected from the time a subject is transplanted with a heart preserved on OCSTM until the completion of the 30-day follow-up evaluation. A heart graft-related adverse event will be followed until resolution or stabilization of the event.

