8.3. Anticipated and Unanticipated Adverse Events

The investigator will assess each adverse event for whether it is anticipated or unanticipated. An unanticipated adverse event is defined as any adverse effect on health or safety, or any life-threatening problem or death caused by, or associated with, a device if that effect, problem or

death was not previously identified in nature, severity or degree of incidence in the investigational plan or application (including a supplementary plan or application), or any other unanticipated serious problem associated with a device that relates to the safety, or welfare of subjects.

Adverse events are associated with heart transplant procedures and have been documented within the first 30 days after heart transplant and are, therefore, anticipated. The list of events includes, but is not limited to:

- Acute rejection
- Atrial and ventricular arrhythmias
- Bleeding (major)
- Hemodynamic instability
- Death
- Fever
- Primary Graft Dysfunction
- Respiratory failure
- Graft failure
- Sepsis
- Renal dysfunction
- Hyperammonaemia
- Malignancy (post-transplant lymphoproliferative disorder (PTLD)
- Multiple organ failure
- Myocardial infarction
- Neurological dysfunction
- Hepatic dysfunction
- Diabetes due to steroid and anti-rejection medications
- Gall stones
- Pancreatitis
- Peptic ulceration
- Gastritis
- Gastro esophageal reflux disease (GERD)
- Aspiration
- Cardiac tamponade
- Pneumo-mediastinum
- Pneumothorax
- Hemothorax
- Pleural bleeding
- Pleural effusion
- Venous thromboembolism (deep venous thrombosis [DVT])
- Pulmonary embolism (PE)
- Sternal wound dehiscence
- Organ deemed not transplantable after retrieval
- Stroke
- Psychosis
- Cerebrovascular accident
- Peripheral vascular clotting or occlusion due insertion of mechanical support

- Limb gangrene due to vascular occlusion due insertion of mechanical support
- Use of mechanical circulatory support
- Coagulopathy
- Hyperacute rejection
- Anastomic site complications; narrowing, bleeding or occlusion
- Delayed sternal wound closure due to compromised cardiac function or excessive bleeding or both
- Bowel thromboembolic complications and gangrene
- Protamine and other anti-heparin medication reaction
- Heparin induced thrombocytopenia

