8.5. Recording and Reporting of Adverse Event

All heart graft-related adverse events and serious adverse events are to be recorded on the electronic case report forms until post-transplant day 30. The description of the adverse event will include: the date of onset, duration, severity, seriousness, the relationship of the event to the trial treatment, anticipated or not, and any treatment required. All serious adverse events occurring during the course of the first 30 days post-transplant will be reported to TransMedics, Inc., as well as documented on the appropriate electronic case report form(s). For all SAEs, the investigator is required to supply any additional data that may be deemed necessary by the Sponsor. Additionally, any serious adverse events (SAE) and unanticipated adverse device effects (UADE) should be reported to TransMedics, Inc., preferably within 48 hours of the time the investigator learns of the event, but in no case later than 5 working days. Heart graft-related AEs will be recorded up to the 30-day follow-up or through hospital discharge if longer than 30 days. For any particular patient, the Independent Medical Monitor if required to protect patient safety may specify a different follow-up period. The Sponsor is responsible for the classification and reporting of heart graft-related adverse events to the appropriate regulatory authorities, and for the on-going safety evaluation of the trial in accordance with ISO 14155 and governing regulatory requirements.

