4.4 Safety Endpoint

The safety endpoint is the number of heart graft-related serious adverse events in the first 30 days post-transplantation per subject. This endpoint is defined to consist of the following adverse events (at most one per type), if they are serious adverse events:

- Moderate or severe Primary Graft Dysfunction (PGD) (left or right ventricle) (not including rejection or cardiac tamponade). Please see Appendix 2 of the protocol for detailed definitions of LV and RV PGD according to ISHLT consensus manuscript.
- Primary graft failure requiring re-transplantation.

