7.0 SUBJECT AND DONOR HEART DISPOSITION

The numbers of subjects in the following categories will be presented in Table 1.1:

- Signing the informed consent
- Not matched with an EXPAND heart
- Matched with an EXPAND heart
- Matched with an EXPAND heart turned down after OCS™
- Matched with an EXPAND heart accepted for transplant after OCS™ but not transplanted
- In the Transplanted Recipient Population

The table will also present the number and percentage of Transplanted Recipient Population patients who completed the study, who died on study, who withdrew from the study early, both overall and by time period (before day 30, between day 30 and 6 months, and between 6 months and 12 months), and the reason for withdrawal.

Donor heart disposition and acceptance details will be summarized in Table 1.2 for the OCS™ Heart Population using frequencies and percentages.

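### Recipients whose accepted OCS heart is not implanted fall outside planned AE collection and every safety analysis, and the AE window has three different end-points

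*Protocol*

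**What the plan says.** **Start of the window.** Protocol 8.1 says that heart graft-related "adverse events will be collected from the time a subject is transplanted with a heart preserved on" the OCS, and it defines such events by the function of the transplanted heart. In 8.5, eCRF recording and the 30-day SAE reporting period are both counted from transplant.

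**The interval before implantation.** Protocol 6.5 says "the surgical procedure should not be initiated on the recipient until the donor heart has been clinically accepted", so surgery may start after acceptance and before the graft is in place. Section 6.1 assigns the subject number when the recipient site makes its final decision to transplant. SAP 7.0 plans a disposition row in Table 1.1 beginning "Matched with an EXPAND heart accepted for transplant after" and covering OCS hearts that were then not transplanted. Protocol 8.3 lists "Organ deemed not transplantable after retrieval" among the anticipated events.

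**Who is analysed.** Protocol 9.2.1 and SAP 6.0 base all safety endpoints on the Transplanted Recipient Population. SAP Tables 6.1 to 6.9 all carry that population in their titles. The stopping rule in 14.10 is defined on recipients transplanted with an OCS-treated heart.

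**End of the window.** Section 8.1 collects "until the completion of the 30-day follow-up evaluation". Section 8.5 first fixes post-transplant Day 30, then says "Heart graft-related AEs will be recorded up to the 30-day follow-up or through hospital discharge if longer than 30 days". SAP 4.4 defines the endpoint as "the number of heart graft-related serious adverse events in the first 30 days post-transplantation per subject". The tolerance in 7.2 is plus or minus "3 days of the designated periods expect for the PGD Surveillance in the first 24 hours".

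**The concern.** The protocol's stated safeguard is that the recipient is not operated on until the heart has been accepted on the device. The harm that would test this safeguard is an accepted heart that is then lost or declined once the recipient is committed. The plan foresees that outcome as a count of subjects, but it has no safety population or table in which the clinical consequence would appear. A reader of the final report would learn that such recipients existed, but not what happened to them.

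The second issue concerns ascertainment. Day-30 survival is a component of the primary endpoint and is the stopping-rule variable. If the visit that records it can take place before Day 30, and no further contact is planned until Month 6, status on Day 30 is not confirmed on schedule for a recipient seen early. Sites working from different sentences of 8.1 and 8.5 would also close AE recording at different times.

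**Working it through.** **1. Recipients accepted for but not given an OCS heart.** No arithmetic applies, so the rules are set side by side.

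| Step | Source | Covers this recipient? |
|---|---|---|
| Subject number at the final decision to transplant | Protocol 6.1 | Yes |
| Surgery allowed after acceptance | Protocol 6.5 | Yes |
| Count in Table 1.1 | SAP 7.0 | Yes, number only |
| Notification of deaths, SAEs and UADEs | Protocol 13.2 (SAEs and UADEs also in 8.5) | Yes, no transplant-based start |
| Graft-related AE collection | Protocol 8.1 | No: starts at transplant and needs a transplanted heart |
| 30-day recording and reporting period | Protocol 8.5 | No: counted from transplant |
| Safety endpoint, Tables 6.1 to 6.9 | Protocol 9.2.1; SAP 6.0 | No |
| Stopping rule | Protocol 14.10 | No, by definition |

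The information can reach the sponsor by notification, but no planned table or count takes it further. SAP Listings 11.1 and 11.2 are also titled as post-transplant events.

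**2. End-points of the AE window.**
- 8.1: completion of the 30-day evaluation. With the 7.2 tolerance this is Day 30 − 3 = 27 to Day 30 + 3 = 33.
- 8.5, first statement: Day 30, whatever the visit date.
- 8.5, later statement: 30-day follow-up, or discharge if that is later than 30 days.
- SAP 4.4: first 30 days.

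Because 8.5 records to Day 30 and requires all SAEs of the first 30 days to be reported, the number of SAE days left uncovered after a Day-27 visit is 0. What remains is a disagreement in wording.

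**3. Survival status.** Survival is scheduled at Day 30, Month 6 and Month 12 (Protocol Appendix 3). Section 7.3 allows ±1 month at 6 months, so the next planned contact falls between 6 − 1 = 5 and 6 + 1 = 7 months. After a Day-27 visit, nothing scheduled confirms that the recipient was alive on Days 28, 29 and 30.

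**4. What one death could change.** First, the plan's own figure. For n = 55 and rejection at 42 or more, the exact binomial gives
- P(X ≥ 42 | 55, 0.65) = 0.0489
- P(X ≥ 42 | 55, 0.80) = 0.8032
- 42/55 = 76.4%

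This agrees with Protocol 9.6. At the enlarged size of 75:
- P(X ≥ 56 | 75, 0.65) = 0.0485, which rejects
- P(X ≥ 55 | 75, 0.65) = 0.0799, which does not reject

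One reclassified recipient therefore changes the conclusion only if the count is exactly at the boundary. At the design rate, P(X = 56 | 75, 0.80) = 0.056.

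The stopping rule has the same kind of step. Table 1 in 14.10 continues at 6 deaths in 20 recipients and stops at 7. For this rule the date on which a death becomes known matters, because the bound is recalculated at each death.

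**The case against.** The strongest reply is that the protocol already catches most of this. Section 13.2 requires deaths, SAEs and UADEs to be notified, with no transplant-based start, and 8.5 repeats the reporting times for any SAE or UADE. A recipient awaiting an accepted heart already has a subject number, and the Medical Monitor reviews SAEs over the course of the trial. The organ itself is followed: Appendix 3 collects reasons for non-transplant, SAP Tables 1.1 and 1.2 and Listings 19 and 22 report disposition, and an unimplanted heart counts against the utilization endpoint. This stands. A reader might infer that harm to these recipients goes unrecorded, or that a non-transplantable organ cannot be recorded; the documents support neither. They do support the narrower statement that the recipient's outcome is not systematically collected and enters no safety analysis.

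A reader might also infer from 8.1 alone that SAEs on Days 28-30 are lost, or that 3 of 30 days of the safety window disappear. Section 8.5 rules that out.

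On survival, 7.2 itself says status is assessed on Day 30, and the SAP plans Kaplan-Meier estimates at Day 30, which need dates of death. A death on Days 28-30 would thus be found late rather than missed, and an analysis run after follow-up would include it. That is fair for the final primary analysis. It does not help the stopping rule, and the notification clock in 13.2 runs from when the investigator learns of the death.

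Finally, leaving non-implanted recipients out of the stopping rule follows from its stated definition. That is accepted, and the fix leaves the rule alone.

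**Conclusion.** The point holds in two limited parts.

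First, recipients whose OCS heart is accepted but not implanted are outside the plan's systematic AE collection and outside every planned safety result, although the plan expects that they may occur. The size is unknown because the documents give no frequency. The order of cooling, removal and recipient surgery after acceptance is not spelled out either. The point relies only on 6.5 and on the Table 1.1 category.

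Second, the AE window has three end-points across 8.1 and 8.5, and the ±3-day tolerance allows the only survival contact planned before Month 6 to fall on Day 27. The consequence is possible late knowledge of a death on Days 28-30. It is greatest for a recipient already discharged, and it matters more for the stopping rule than for the final test. It would be wrong to read the pair of p-values as showing that the primary result is under threat: they differ in conclusion only at exactly 56 successes of 75, and the documents give no basis for estimating how many deaths would fall on those days.

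The sample size and error rates are unaffected. The changes are cheap and improve safety reporting and endpoint ascertainment, so they should be made.

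**What to change.** - **Protocol 8.1 and 8.5:** for a consented recipient, start AE and SAE collection at acceptance of the OCS heart or at the start of recipient anaesthesia, whichever comes first, whether or not the heart is then implanted.
- **SAP 13.1:** add one listing of accepted-but-not-transplanted recipients with their SAEs and 30-day outcome. Report any death among them to the DSMB. Leave the stopping-rule definition unchanged.
- **Protocol 8.1, 8.5 and SAP 4.4:** reconcile to a single closing rule, and limit SAP Table 6.1 to events with onset on Days 0-30.
- **Protocol 7.2:** confirm survival and AE status on or after Day 30, for example Day 30 to Day 33. Derive Day-30 survival from the date of death, not from status at the visit.

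The cost is protocol and eCRF wording, one listing, a few extra records for recipients who were not transplanted, and some status calls a few days later.
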